5.3.2 Main Analytical Approach for Primary Virology Endpoint

The primary virology endpoint analyses will be performed on the mITTi population using the nasopharyngeal swab data.

For each cohort, the change from baseline in the amount of SARS-CoV-2 virus RNA will be compared between the AT-527 group and the pooled placebo group (meaning all placebo patients up to and including the cohort being analyzed will be used to form the placebo comparator group) at Days 3, 5, and 7 using analysis of covariance (ANCOVA) with baseline viral load as a covariate.

The least squares mean (LSM) change and its standard error (SE) of means in each group, the difference between two groups in LSM change, SE, and 80% CI, and p-values will be presented. The LSM change will be presented graphically over time.

Additionally, descriptive summaries for the change from baseline will also be presented by treatment group. The change from baseline and the amount of SARS-CoV-2 virus RNA will also be presented graphically over time.

Baseline is defined as the Day 1 (pre-dose) nasopharyngeal swab ([Table 4](#)).

If the data are not normally distributed, a non-parametric alternative method will be used (e.g., Mann-Whitney U test) to compare distributions.

The qualitative result of the SARS-CoV-2 RT-PCR test is determined using cycle threshold (Ct) values. If the qualitative result is positive, then an associated quantitative result is also provided. The quantitative result is either numerical or below the limit of quantification (BLQ). The limit of quantification (LOQ) for the virus RNA is 120 copies/ml. If the virus RNA sample has a positive qualitative result, but a quantitative result BLQ, virus RNA will be imputed as LOQ – 1 (119 copies/mL). Negative qualitative samples will be imputed as LOQ/2 (60 copies/ml) before being transformed to the log10 scale. Samples reported as positive, but not quantifiable, will contribute to qualitative summaries, but will be treated as missing (not imputed) for quantitative summaries.

Missing data will not be imputed. Any missing data will not be included in the analyses.

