4.2 METHOD OF TREATMENT ASSIGNMENT AND BLINDING

4.2.1 Treatment Assignment

This is a randomized, double-blind study. After initial written or electronic informed consent has been obtained, all screening procedures and assessments have been completed, and eligibility has been established for a patient, the study site will obtain the patient's identification number and treatment assignment from an interactive voice or web-based response system (IxRS).

In Cohort A and Cohort E, patients will be randomly assigned to receive AT-527 or placebo in a 1:1 ratio. In Cohorts B–D, patients will be randomized to receive AT-527 or placebo in a 3:1 ratio. A permuted-block randomization method will be utilized to ensure a balanced assignment to each treatment arm (see Section 3.1 for details).

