4.4.1 Permitted Therapy

Patients are permitted to use the following therapies during the study:

- Hormonal contraceptives (see Section 4.1.1)
- Hormone-replacement therapy
- Paracetamol (acetaminophen)
- Non-steroidal anti-inflammatory drugs
- COVID-19 vaccines are permitted from Day 15 onwards (see Section 4.5.2 for documentation requirements pertaining to vaccine type and date of dosing).
 - Patients must have a 40-day window since their last dose of vaccination (second dose if applicable) prior to enrollment.

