4.5.2 Medical History, Baseline Conditions, Concomitant Medication, and Demographic Data

Medical history, including clinically significant diseases, surgeries, cancer history (including prior cancer therapies and procedures), reproductive status, smoking history, and use of alcohol and drugs of abuse, will be recorded at baseline. In addition, all medications (e.g., prescription drugs, over-the-counter drugs, vaccines, herbal or

homeopathic remedies, nutritional supplements) used by the patient within 7 days prior to initiation of study treatment (12 months for COVID-19 vaccines) will be recorded. At the time of each study visit and at the follow-up telephone call (Day 33), an interval medical history should be obtained and any changes in medications and allergies should be recorded.

Demographic data will include age, sex, and self-reported race/ethnicity.

COVID-19 vaccines should be reported by the brand name or company manufacturer, if available (examples: Pfizer COVID-19 vaccine, Moderna COVID-19 vaccine) and date administered if known. If not available, report as COVID-19 vaccine.

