6.4.1 Primary Virology Endpoint

The primary objective of this study is to evaluate the antiviral activity of AT-527 compared with placebo on the basis of the change from baseline in amount of SARS-CoV-2 virus RNA as measured by RT-PCR and based on the log-10 scale at specified timepoints.

In Cohorts A-D, the change from baseline in the amount of SARS-CoV-2 virus RNA will be compared between each AT-527 group and a combined placebo group at Days 3, 5, and 7 using Analysis of Covariance (ANCOVA) with baseline virus RNA as a covariate. The treatment group least squares mean (LSM) changes, difference in LSM changes, 80% CI and p-value will be presented for each comparison. Additionally, descriptive summaries for the change from baseline will also be presented by treatment group.

In Cohort E, the change from baseline in the amount of SARS-CoV-2 virus RNA will be compared between the AT-527 group and a placebo group containing only patients from Cohort E (unpooled) at Days 3, 5, 7, and 14 using Analysis of Covariance (ANCOVA) with baseline virus RNA as a covariate. The treatment group least squares mean (LSM) changes, difference in LSM changes, 95% CI and p-value will be presented for each comparison. Additionally, descriptive summaries for the change from baseline will also be presented by treatment group.

If the data are not normally distributed, a non-parametric alternative method will be used (e.g., Mann-Whitney U test) to compare distributions.

Further details of the primary endpoint analysis will be included in the SAP, including details of any missing data handling rules for the primary endpoint.

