Appendix 1: Schedule of Activities for Cohort A

chemistry panel (serum or plasma) includes bicarbonate or total carbon dioxide (if considered standard of care for the region), sodium, potassium, chloride, glucose, BUN or urea, creatinine, total protein, albumin, phosphate, calcium, magnesium, total and direct bilirubin, ALP, ALT, AST, urate, CK (isoenzyme analysis if CK elevated), cardiac troponins, BNP, triglycerides, cholesterol, amylase, LDH, PCT, and lipase.

- ⁿ All women of childbearing potential will have a pregnancy test (*urine or serum*) at screening.
- ^o Nasopharyngeal swab samples should be collected at screening and once per day on Days 1, 3, 5, and 7. Swab samples should be collected from both nostrils at all timepoints. Screening samples will be used for point-of-care RT-PCR or rapid antigen testing to determine eligibility.
- ^p Sample must be collected prior to dosing.
- ^q Randomization will be performed as soon as possible after screening and within 72 hours.
- ^r First dose on Day 1 must be administered as soon as possible after randomization and within 24 hours. AT-527 (or placebo), should be taken approximately 12 hours apart. If the first dose is taken after 4 pm (16:00 hours) on Day 1, the next dose will be taken in the morning of Day 2. For these patients, the 10th dose will be taken on the morning of Day 6. If the first dose is taken prior to 4 pm (16:00 hours) on Day 1, the next dose should be taken in the evening of the same day (i.e., prior to midnight on the same calendar day with a minimum of 8 hours between doses). For these patients, the 10th dose will be taken in the evening of Day 5.
- ^s Medication (e.g., prescription drugs, over-the-counter drugs, vaccines, herbal or homeopathic remedies, nutritional supplements) used by a patient in addition to protocol-mandated treatment from 7 days prior to initiation of study drug until the end of study follow-up telephone call on Day 33.
- ^t After informed consent has been obtained but prior to initiation of study drug, only serious adverse events caused by a protocol-mandated intervention should be reported. After initiation of study drug, all adverse events will be reported until the end of study follow-up telephone call on Day 33.

Appendix 2
Schedule of Activities for Cohorts B–D

	Screening ^a	Treatment					Monitoring					UV ^b	ET ^c	Follow-up	
		Day	–3 to 1	1	2	3	4	5	6	7	8–13	14 ^d	15–28		
Informed consent	x ^{e, f}														33 ^d (±3)

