5.3.5 Subgroup Analyses for Primary Virology Endpoint

The change from baseline in the amount of SARS-CoV-2 virus RNA may be compared between the treatment groups and pooled placebo group for the following subgroups:

- Baseline viral load (for example: high, low; based on median baseline viral load)
- Baseline anti-SARS-CoV-2 antibody (spike protein) status (positive, negative)
- Time from symptom onset to treatment (≤ 3 days, > 3 days)
- Any underlying health conditions (yes, no)

Subgroup analyses will be analyzed descriptively at each timepoint and may be plotted over time.

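### The primary ANCOVA leaves out baseline antibody status and time from symptom onset, both obtained before dosing, and so gives up some precision and protection against chance imbalance.

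*SAP*

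**What the plan says.** **Model.** SAP 5.3.2 compares the arms "using analysis of covariance (ANCOVA) with baseline viral load as a covariate". Protocol 6.4.1 does so "using Analysis of Covariance (ANCOVA) with baseline virus RNA as a covariate", for Cohorts A-D and again for Cohort E. If the data are not normal, both switch to a non-parametric test such as Mann-Whitney.

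**Randomisation.** Protocol 4.2.1: "A permuted-block randomization method will be utilized to ensure a balanced assignment to each treatment arm". Neither it nor SAP 1.2.1 names a stratification factor.

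**What is collected.** Appendices 1-3 of the protocol schedule antibody serum on Day 1 before dosing in every cohort. Symptom onset must fall within 5 days before randomisation (4.1.1) and is tabulated at baseline (6.3; SAP 5.7.3).

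**How it is used.** SAP 5.3.5 lists as a subgroup for the primary endpoint "Baseline anti-SARS-CoV-2 antibody (spike protein) status (positive, negative"), together with time from symptom onset to treatment, split at 3 days. These comparisons are optional and descriptive. SAP 5.7.1 includes them in the Day 10 review only if the data are available.

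**Vaccination.** Protocol 4.5.2 has medicines taken "within 7 days prior to initiation of study treatment (12 months for COVID-19 vaccines) will be recorded". SAP 5.7.3 summarises previous and concomitant treatments by treatment group. Protocol 4.4.1 adds: "Patients must have a 40-day window since their last dose of vaccination (second dose if applicable) prior to enrollment".

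**The concern.** Viral load falls without treatment in this infection, as Protocol 3.3.3 says. Two patients with the same Day 1 load may clear virus at different speeds if one already has antibody or presented later. If so, baseline load alone leaves explainable variation in the residual. The interval is then wider than it need be, and an unlucky split of immune patients between small arms shifts the estimate with no correction in the model. The two factors concerned are measured before treatment, and the SAP itself treats them as worth examining for this endpoint.

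**Working it through.** **Inputs (Protocol 6.1).** Cohorts A-D: 27 evaluable per arm, difference 0.7-1.1 log10, SD 1.2-1.85, one-sided alpha 10%. Cohort E: 100 evaluable per arm, difference 0.5, SD 1.25, one-sided alpha 2.5%. Both assume that 90% are evaluable. The SAP still describes Cohort E as 40 patients randomised 3:1, so the Cohort E figures here are the protocol's.

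**Step 1: the plan's own figures.** Power = Φ(δ / [SD × √(2/n)] − z).
- A-D, 0.7 with SD 1.2: SE = 1.2 × √(2/27) = 0.327. Power = Φ(2.143 − 1.282) = 80.6%. The n needed for 80% is 27.
- A-D, 1.1 with SD 1.85: power 81.7%, n = 26.
- E: SE = 1.25 × √(2/100) = 0.177. Power = Φ(2.828 − 1.960) = 80.7%, n = 99.
- 27/0.9 = 30 and 100/0.9 = 111.1, rounded up to 112.

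The plan's sample sizes are reproduced.

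**Step 2: assumptions.** The documents give neither the share of patients with pre-existing immunity (p) nor its effect on the decline at a given baseline load (b). I take p = 20-50% and b = 0.25-1.0 log10, and treat the planning SD as the residual SD of the current model.

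**Step 3: gain from one binary immunity term.** Residual SD = √(SD² − p(1−p)b²).

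| Design case | b | p | Residual SD | Power | n per arm for 80% |
|---|---|---|---|---|---|
| A-D, SD 1.2 | 0.25 | 20% | 1.196 | 80.8% | 27 |
| A-D, SD 1.2 | 0.5 | 50% | 1.174 | 81.9% | 26 |
| A-D, SD 1.2 | 1.0 | 50% | 1.091 | 85.9% | 22 |
| A-D, SD 1.85 | 0.25 | 20% | 1.847 | 81.8% | 26 |
| A-D, SD 1.85 | 1.0 | 50% | 1.781 | 83.8% | 24 |
| E, SD 1.25 | 0.25 | 20% | 1.246 | 81.0% | 98 |
| E, SD 1.25 | 0.5 | 50% | 1.225 | 82.3% | 95 |
| E, SD 1.25 | 1.0 | 50% | 1.146 | 87.0% | 83 |

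No separate gain was computed for time from onset.

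**Step 4: chance imbalance.** The SD of the between-arm difference in prevalence is √(2p(1−p)/n). For p = 20-50% this is 0.109-0.136 with 27 per arm and 0.057-0.071 with 100 per arm. A difference of 10 points or more then has probability 36-46% in Cohort A and 8-16% in Cohort E. If the split favours AT-527 and b = 0.5:
- Cohort A, 20 points: shift 0.2 × 0.5 = 0.10 log10. One-sided error given that split is 1 − Φ(1.282 − 0.10/0.327) = 16.5%, against 10%.
- Cohort E, 10 points: shift 0.05 log10. Error given that split is 1 − Φ(1.960 − 0.05/0.177) = 4.7%, against 2.5%.

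**Step 5: type I error over all splits.** With p = 35% and b = 1.0 left unadjusted, simulation gave a one-sided error of 9.9% for Cohort A and 2.5% for Cohort E. Both are nominal.

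**The case against.** The strongest reply is that nothing here is invalid. Concurrent 1:1 randomisation balances immunity in expectation, and chance imbalance is already inside the standard errors of 0.327 and 0.177. Step 5 confirms this. The raised errors in step 4 apply only once an unfavourable split has occurred; favourable and unfavourable splits cancel over repetition. The study also calls itself hypothesis-generating, and entry within 5 days of onset already narrows the spread in presentation time. All of this stands, and it limits the point to precision and robustness.

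Some stronger readings are tempting:
- A reader might infer that the estimate is biased because randomisation is unstratified. In Cohorts A and E it is not.
- A reader might take the 41.1% global vaccine coverage in Protocol 1.1 as the trial's prevalence of immunity. It is a population figure, and the same sentence gives 1.9% for low-income countries.
- A reader might infer that vaccination enters no analysis. Protocol 4.4 counts vaccines as concomitant therapy, and SAP 5.7.3 summarises such treatments by arm.
- A reader might see the 40-day window as proof that the sponsor regards vaccination as driving viral course. Section 4.4.1 gives no reason for the window.
- A reader might extend the point to bias in Cohorts B-D, where placebo is pooled across sequential cohorts. Randomisation does not protect that comparison in the same way, but a bias requires immunity to drift between cohorts, and the documents give no prevalence by cohort. That is a separate question about non-concurrent controls.

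A practical objection also stands. Antibody serum goes to a central laboratory (Protocol 4.5.5), so results may not be ready for the Day 10 or Day 14 review.

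**Conclusion.** The point holds as a missed, inexpensive gain. The primary model omits two pre-treatment factors that the SAP already considers relevant to the endpoint. Under the assumed ranges, adjusting for immunity adds between a fraction of a point and about 5 points of power in the A-D case with SD 1.2 (80.6% to 80.8-85.9%), at most about 2 points with SD 1.85 (81.7% to 81.8-83.8%), and up to about 6 points in Cohort E (80.7% to 81.0-87.0%). The upper ends need an effect near 1 log10 and a prevalence near 50%. The gain shrinks if baseline viral load already carries part of the effect. The documents supply neither prevalence nor effect, so the size is conditional on these assumptions. The absence of the two terms from the model does not depend on them.

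**What to change.** 1. In SAP 5.3.2 and Protocol 6.4.1, specify the primary ANCOVA with baseline viral load, baseline anti-spike antibody status (positive, negative, missing) and time from symptom onset to treatment (3 days or less, more than 3 days). Keep the viral-load-only model as a sensitivity analysis.
2. State that if central serology is not available at the Day 10 or Day 14 review, the viral-load-only model is reported then and the adjusted model follows when results arrive.
3. Note that the Mann-Whitney fallback carries no covariates, so this adjustment does not apply there.

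The cost is SAP and protocol wording, dependence on serology timing, and two or three degrees of freedom: one for onset, one for antibody status, and one more if any status is missing. With 54 evaluable patients, residual degrees of freedom fall from 51 to 49 or 48. No new data are needed. Showing prior vaccination in the baseline table would be clearer presentation only.

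Two drafting matters are separate from the model. The 40-day statement in Protocol 4.4.1 applies before enrolment but is absent from the criteria in 4.1.1 and 4.1.2. The Cohort A footnote in Appendix 1 covers medication in addition to "protocol-mandated treatment from 7 days prior to initiation of study drug until the end of study", without the 12-month vaccine look-back in 4.4 and 4.5.2. Each set of passages must be reconciled.

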6.1 DETERMINATION OF SAMPLE SIZE

The primary objective of this study is to evaluate the antiviral activity of AT-527 compared with placebo. Approximately 60 patients will be randomized in a 1:1 ratio in Cohort A to receive AT-527 or placebo. Cohorts B–D will enroll approximately 40 patients in a 3:1 ratio to receive AT-527 or placebo, respectively. *Cohort E will enroll approximately 224 patients in a 1:1 ratio to receive AT-527 or placebo.*

The sample size for Cohort A–D is based on the primary endpoint of change from baseline in SARS-CoV-2 virus RNA measured by RT-PCR at a single timepoint. A sample size of 27 patients per arm (active or placebo) in the mITTi population will result in at least 80% power to detect a mean reduction in change from baseline of between 0.7 and 1.1 log₁₀ copies using a two-sample t-test for comparison of means, assuming a standard deviation of between 1.2 and 1.85 (Regeneron 2020) and based on a 1-sided 10% alpha. The sample size has been adjusted to 30 patients per arm to account for an estimated 90% SARS-CoV-2 positive rate and is based on a single-cohort comparison of AT-527 versus placebo.

For Cohort E, a sample size of 100 patients per arm (active or placebo) in the mITTi population will result in at least 80% power to detect a mean reduction in change from baseline of 0.5 log₁₀ copies using a two-sample t-test for comparison of means, assuming a standard deviation of 1.25 (deemed appropriate based on current data from WV43042) and based on a 1-sided 2.5% alpha. The sample size for Cohort E has been adjusted to 112 patients per arm to account for an estimated 90% SARS-CoV-2 positive rate. Based on emerging external data on direct acting antivirals in COVID-19 (Fischer et al 2021), a lower mean reduction in change from baseline of 0.5 log₁₀ copies has been utilized in Cohort E. A lower alpha level has also been selected to reduce the likelihood of a false positive result and enable a more robust evaluation of the antiviral activity of AT-527 at the selected dose regimen. This sample size also allows for a better characterization of the secondary endpoints.

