6.4 VIROLOGY AND EFFICACY ANALYSES

All virology and efficacy analyses will be performed on the mITTi population.

Sensitivity analyses to evaluate the robustness of results to the primary analysis methods (e.g., handling of dropouts) may be conducted and will be described in the SAP.

No alpha adjustments for multiple comparisons are planned.

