3. SAMPLE SIZE DETERMINATION

The primary objective of this study is to evaluate the antiviral activity of AT-527 compared with placebo. Approximately 60 patients will be randomized in a 1:1 ratio in Cohort A to receive AT-527 or placebo. Each additional cohort will enroll approximately 40 patients in a 3:1 ratio to receive AT-527 or placebo, respectively.

The sample size is based on the primary endpoint of change from baseline in SARS-CoV-2 virus RNA measured by RT-PCR at a single timepoint. A sample size of

27 patients per treatment group (active or placebo) in the modified intent-to-treat infected (mITTi; defined in [Table 2](#)) population will result in at least 80% power to detect a mean reduction in change from baseline of between 0.7 and 1.1 log₁₀ copies using a two-sample t-test for comparison of means, assuming a standard deviation of between 1.2 and 1.85 (Regeneron 2020) and based on a 1-sided 10% alpha. The sample size has been adjusted to 30 patients per treatment group to account for an estimated 90% SARS-CoV-2 positive rate and is based on a single-cohort comparison of AT-527 versus placebo.

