5.3.3 Sensitivity Analyses for Primary Virology Endpoint

A sensitivity analysis may be performed, whereby only data obtained at the nominal timepoint is used. This means that the time windows in [Table 4](#) would not be applicable; only samples collected on the scheduled timepoints (Days 3, 5, and 7) would be included in the analysis.

At the end of the study, sensitivity analyses will also be performed for each cohort with a combined placebo group from all cohorts.

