5.3.4 Supplementary Analyses for Primary Virology Endpoint

To supplement the main analysis, an exploratory time-weighted average change from baseline may also be performed. This will be calculated as the AUC of the change from baseline viral load divided by its total time interval (time of last observation minus time of first observation).

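### The normality-triggered fallback from the primary ANCOVA leaves its trigger, method and estimate open, and the one example it names drops the planned baseline covariate

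*SAP*

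**What the plan says.** SAP 5.3.2 compares change from baseline in log10 viral RNA at Days 3, 5 and 7 by ANCOVA with baseline viral load as covariate. As output, "the difference between two groups in LSM change, SE, and 80% CI, and p-values will be presented". Later in the same section comes the fallback: "If the data are not normally distributed, a non-parametric alternative method will be used (e.g., Mann-Whitney U test) to compare distributions". Protocol 6.4.1 and the Synopsis word it identically. In Protocol 6.4.1 it follows the Cohort E paragraph, which adds Day 14 and a 95% CI.

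Protocol 6.4.1 passes the detail on: "Further details of the primary endpoint analysis will be included in the SAP". The SAP repeats the sentence and adds no rule. Protocol 6.4 allows for robustness work: "Sensitivity analyses to evaluate the robustness of results to the primary analysis methods (e.g., handling of dropouts) may be conducted". What the SAP then lists is:

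- SAP 5.3.3: "A sensitivity analysis may be performed, whereby only data obtained at the nominal timepoint is used", plus a rerun with placebo pooled from all cohorts.
- SAP 5.3.4: "To supplement the main analysis, an exploratory time-weighted average change from baseline may also be performed".
- SAP 5.3.5: optional descriptive subgroups, one of them by baseline viral load.

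None of these keeps the ANCOVA if the fallback is invoked, or defines the fallback further.

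**The concern.** Five things are left open: the quantity checked (raw change, change within arm, or ANCOVA residuals), the criterion, the level at which it applies (visit or cohort), the final method, since Mann-Whitney is only an example, and the estimate with CI that accompanies it. Two statisticians following the sentence faithfully could report different primary analyses, only one of them with a defined effect size.

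The choice of quantity matters because SAP 5.3.2 sets negatives to 60 copies/mL and positive results below the 120 copies/mL limit to 119. As patients clear virus, follow-up values pile up at two points. That can make ANCOVA residuals clearly non-normal while raw change scores still pass a normality test. At stake are the precision bought by the baseline covariate and a primary result that is fully defined before the data are seen.

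**Working it through.** **The plan's own sizing.** Power of a one-sided two-sample t-test, with noncentrality = effect / (SD × √(2/n)):

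- Cohorts A–D (SAP 3, Protocol 6.1), n = 27, one-sided 10%: 0.7 / (1.2 × √(2/27)) = 2.14, power 80.1%. With effect 1.1 and SD 1.85, power is 81.2%. 27/0.9 = 30.
- Cohort E (Protocol 6.1), n = 100, one-sided 2.5%: 0.5 / (1.25 × √(2/100)) = 2.83, power 80.4%. 100/0.9 = 111.1, rounded up to 112.

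Both stated sizes reproduce. Both rest on an unadjusted t-test: "two-sample t-test for comparison of means, assuming a standard deviation of between 1.2 and 1.85" for A–D, and for E "assuming a standard deviation of 1.25 (deemed appropriate based on current data from WV43042) and based on a 1-sided 2.5% alpha".

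**What the covariate adds without flooring.** If baseline and change correlate at r (not given in the documents), adjustment shrinks the SD by √(1 − r²). Simulated Cohort E power at r = 0, −0.3, −0.5, −0.7 is 81%, 84%, 90%, 98% for ANCOVA and 78–80% throughout for Mann-Whitney on change scores.

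**With flooring.** Simulation, 5,000 trials per row, 100 per arm, true effect 0.5, one-sided 2.5%. From the documents: sample size, effect, alpha, change SD 1.25, and imputation at 60 and 119 copies/mL. Assumed: baseline mean 6.0 and SD 1.4 log10; placebo follow-up mean 5.0 (first three rows) or 3.2 (last three); detection limit 1.3 log10; baseline-to-follow-up slope b; trigger a 5% Shapiro-Wilk test. Residual SD = √(1.25² − (1 − b)² × 1.4²), which is 1.08, 1.18, 1.22 at b = 0.55, 0.7, 0.8. Floored means a follow-up value below 120 copies/mL.

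| b | Floored | ANCOVA | t-test | Mann-Whitney | ANCOVA minus M-W | Rank ANCOVA | Residual trigger fires | Power with residual trigger |
|---|---|---|---|---|---|---|---|---|
| 0.55 | 2.4% | 90.3% | 80.2% | 77.9% | 12.4 | 87.6% | 6% | 89.6% |
| 0.7 | 4.3% | 83.8% | 79.2% | 77.1% | 6.7 | 81.7% | 8% | 83.3% |
| 0.8 | 5.6% | 81.3% | 78.7% | 76.7% | 4.6 | 78.2% | 9% | 80.9% |
| 0.55 | 25.8% | 87.4% | 63.6% | 61.9% | 25.5 | 87.6% | 85% | 65.6% |
| 0.7 | 28.7% | 78.6% | 62.9% | 60.7% | 17.9 | 79.5% | 81% | 64.0% |
| 0.8 | 30.2% | 75.0% | 63.4% | 61.9% | 13.1 | 77.0% | 78% | 64.4% |

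Repeat runs put the first gap at 5–11 points and the second at 15–23 or 16–27, so the ends of these ranges are good to a few points.

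**Trigger on change scores.** The same test on pooled change scores fires in 5–6% of trials in all six rows and costs at most about 1.4 points. Over a wider grid (slope down to 0.3, up to 56% floored) the cost is about 2–3 points, 3.8 in the worst cell; testing each arm separately gave at most 4.8.

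**Cohort A sizing** (27 per arm, effect 0.7, one-sided 10%, residual SD 1.15, slopes 0.3–0.8, 27–32% floored). ANCOVA has 76–80% power against 52–64% for Mann-Whitney; the residual trigger fires in 25–51% of trials.

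**Type I error.** With trigger and method fixed beforehand: 2.3–2.6% (nominal 2.5%) and 9.6–10.6% (nominal 10%). Taking the smaller p-value after seeing both: 3.3–4.6% and 12–17%.

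**The case against.** The best defence is that SAP 5.3.2 promises the LSM difference and CI without condition, so the fallback may only add a comparison of distributions. The text allows this, and a reader who infers that the plan withdraws the LSM output goes too far. But a rule that an alternative will be used reads most naturally as replacement, and the plan should not need that inference.

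Other points stand in whole or part:

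- The method is not fixed, rather than unnamed. Mann-Whitney on change scores still uses baseline by subtraction; only the covariate adjustment is lost.
- A reader might infer that the fallback breaks the 80% power. It does not. Mann-Whitney stays within 3 points of the t-test used for sizing in every row. The fall below 80% at 26–30% floored comes from the floor, and the switch forgoes only a covariate gain that the plan never claimed.
- The large losses need heavy flooring and the residual reading together. The floored share, slope and baseline distribution are not in the documents. Still lower Mann-Whitney power (28–42% at 53–54% floored) comes from even heavier flooring, and its low end from slope 0.3, where the change SD is about 1.5 rather than the planned 1.25.
- The figures depend on imputing positive, non-quantifiable samples at 119. With those treated as missing, at 24–30% floored and residual SD 1.15, the residual trigger fired in 49–80% of trials instead of 72–99%, and ANCOVA power was 74–75% instead of 80–84%. SAP 5.3.2 has conflicting sentences on these samples; that is a separate matter and does not support this point.
- The study is called hypothesis-generating, and the SAP still describes Cohort E as 40 patients at 3:1, so Cohort E detail could come with a SAP update. That lowers the stakes but does not supply the rule for Cohorts A–D.

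**Conclusion.** The concern holds as a gap in specification together with a poorer example method. It is worth correcting and does not threaten the trial's validity. Nothing in Protocol 6.4 or SAP 5.3.3–5.3.5 supplies the trigger, the final method or the accompanying estimate.

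Relative to the planned ANCOVA, using Mann-Whitney gives up roughly 5–12 points of power with 2–6% floored and roughly 13–26 points with 26–30% floored, at change SD 1.25 and slopes 0.55–0.8. Read as a test on change scores, the rule loses about 2–3 points at most. Read as a test on residuals, it fires in most Cohort E trials once about a quarter of values are floored, and most of the gap is realised. These are ranges under assumed inputs, not predictions for this trial.

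A reader might also infer an inflated false-positive rate. The documents do not support that: error stays nominal if trigger and method are fixed beforehand, and neither document describes choosing after seeing both results. The wording simply does not rule that out.

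**What to change.** Delete the normality-triggered sentence from SAP 5.3.2, Protocol 6.4.1 and the Synopsis. Keep baseline-adjusted ANCOVA as primary at every visit, with the LSM difference and the planned interval: 80% for Cohorts A–D, 95% for Cohort E. In SAP 5.3.3, pre-specify one sensitivity analysis in place of Mann-Whitney: rank ANCOVA, regressing ranks of follow-up load on treatment and ranks of baseline load. Baseline load is already collected.

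The cost is wording in two documents and one extra table. In the simulations rank ANCOVA was at most about 3 points below ANCOVA, and 3–8 points above it at 53–57% floored. It uses only the order of follow-up values, so the exact imputed figure for negatives does not affect it.

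The downside of unconditional ANCOVA is that its LSM difference shrinks toward zero when many values are floored: about 0.37–0.40 for a true 0.5 at 24–30% floored. Rank ANCOVA gives no log10 estimate of its own, but it helps show whether a small LSM difference reflects the floor.

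If the sponsor prefers to keep a fallback, make it baseline-adjusted and state the quantity checked, the criterion, the level (visit or cohort), the single method, and its estimate with CI. Reconcile the sentences on positive, non-quantifiable samples separately.
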